10.5.2 Solicited AEs

Solicited local AEs (injection site pain, redness, swelling and itching) and solicited systemic AEs (chills, fever, nausea/vomiting, diarrhea, headache, fatigue, myalgia and arthralgia) information is collected for subjects in the Immunogenicity/Reactogenicity Subset for each day of vaccination (i.e. dose 1 and dose 2) and for the following 7 days after each dose. Subjects record any occurrence of an AE, grading of severity, and medication for treatment of the AE in an electronic diary (eDiary).

Subjects' eDiaries are reviewed by the investigator and available information on solicited local and systemic AEs with a grade > 0 is integrated into the CRF, including assessment of severity on an intensity scale of mild, moderate, and severe (Grade 1 – Grade 3), see Table 5 and Table 6. Note that events with a severity Grade 0 are not recorded as AEs in the CRF.

Additional solicited AEs may be recorded by the investigator based on CRF review if the recording within the diary is deemed incomplete.

In case there is more than one solicited AE with the same relationship to study treatment on a specific day with the same type of reaction (e.g. myalgia, injection site pain, nausea/vomiting) but recorded as different events, records are collapsed for that specific diary day. Thereby, if there are overlapping events with the same relationship on a given diary day, they are collapsed and reported with the highest severity grade on that day. Overlapping events with different relationship to study treatment are not collapsed.

Solicited events reported as "Nausea" and "Vomiting" are considered to be of the same reaction type "Nausea/Vomiting".

Table 5: Intensity Grading* for Solicited Local Adverse Events

AE	Grade	Definition
Pain at injection site	0	Absent
	1	Does not interfere with activity
	2	Interferes with activity and/or repeated use of non-narcotic pain reliever >24 hours
	3	Prevents daily activity and/or repeated use of narcotic pain reliever
Redness	0	<2.5 cm
	1	2.5 – 5 cm
	2	5.1 – 10 cm
	3	>10 cm
Swelling	0	<2.5 cm
	1	2.5 – 5 cm and does not interfere with activity

AE	Grade	Definition
	2	5.1 – 10 cm or interferes with activity
	3	>10 cm or prevents daily activity
Itching	0	Absent
	1	Mild, no interference with normal activity
	2	Moderate, some interference with normal activity
	3	Significant, prevents normal activity

* FDA toxicity grading scale

Solicited AEs are assigned to first or second dose based on the (reported or imputed) AE date. Solicited AEs occurring before dose 2 are assigned to dose 1. Solicited AEs occurring on or after dose 2, are assigned to dose 2.

Solicited local AEs are always considered related to trial vaccine. Relationship to trial vaccine for solicited systemic AEs is assessed by the investigator and recorded on the CRF.

If not stated otherwise, data as recorded on the CRF is used for analysis of solicited AEs. However, subject's diary data is used to assess their eligibility for the SASsol (see Section 9.5.3) as follows:

- If at least one question on occurrence of a local or systemic AE is answered with either “Yes” or “No”, then the subject is included in the SASsol.
- If no question on occurrence of a local or systemic AE is answered with either “Yes” or “No”, then the subject is **not** included in the SASsol.

It should be noted that the inclusion in the SASsol is defined overall, not by trial vaccine dosing. I.e. if a subject provided information on solicited AEs for the time period after the second vaccination, but not for the time period after the first vaccination, the subject is still included in the SASsol.

Table 6: Intensity Grading* for Solicited Systemic Adverse Events

AE	Grade	Definition
Fever	0	<38°C
	1	≥38.0 – 38.4°C
	2	≥38.5 – 38.9°C
	3	≥39°C
Headache	0	Absent
	1	Mild, no interference with normal activity
	2	Moderate, some interference with normal activity and/or repeated use of non-narcotic pain reliever >24 hours
	3	Significant; any use of narcotic pain reliever and/or prevents daily activity
Fatigue	0	Absent
	1	Mild, no interference with normal activity
	2	Moderate, some interference with normal activity
	3	Significant, prevents normal activity
Chills	0	Absent
	1	Mild, no interference with normal activity
	2	Moderate, some interference with normal activity
	3	Significant, prevents normal activity

AE	Grade	Definition
Myalgia	0	Absent
	1	Mild, no interference with normal activity
	2	Moderate, some interference with normal activity
	3	Significant, prevents normal activity
Arthralgia	0	Absent
	1	Mild, no interference with normal activity
	2	Moderate, some interference with normal activity
	3	Significant, prevents normal activity
Nausea/ Vomiting	0	Absent
	1	Mild, no interference with activity and/or 1 – 2 episodes/ 24 hours
	2	Moderate, some interference with activity and/or >2 episodes/ 24 hours
	3	Significant, prevents daily activity, requires outpatient i.v. hydration
Diarrhea	0	Absent
	1	2 – 3 loose stools over 24 hours
	2	4 – 5 stools over 24 hours
	3	6 or more watery stools or >800 g/24 hours or requires outpatient IV hydration

* FDA toxicity grading scale; i.v. = Intravenous.

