### **10.3.9 Missing Data**

Analysis of vaccination variables will be done on a valid case basis, i.e., for missing observations, no imputation for missing data, such as last observation carried forward, will be applied.

For SARS-CoV-2 RBD of the S protein antibodies and neutralizing antibodies, concentration/titer values marked as below the LLOQ will be set to  $0.5 \times \text{LLOQ}$ .

No imputation of missing values will be done for any analysis (except the imputation for missing partial dates of AEs and concomitant medication as specified in the SAP).

Currently no replacement of drop-out subjects is foreseen.

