9.5.3 Safety Analysis Subsets (SAS 2 and SASsol)

- The SAS 2 includes all subjects of the SAS who belong to the Immunogenicity/Reactogenicity cohort.
- The SASsol includes all subjects of the SAS who belong to the Immunogenicity/Reactogenicity cohort with at least 1 diary collection indicating the occurrence or lack of occurrence of solicited AEs (see Section 10.5.2).

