12.6 Safety Analyses

12.6.1 Adverse Events

Unsolicited AEs, including SAEs, and AESIs and solicited AEs integrated to or recorded on the CRF are coded using MedDRA Version 23.1 or higher by SOC and PT.

Only TEAEs as defined in Section 10.5.1 are included in AE summaries. In AE listings, all AEs are included.

Solicited AEs occurring on the day of vaccination and the following 7 days are generally included in summaries if not otherwise stated.

Summaries of medically attended AEs only include those AEs that started up to 6 months after the second trial vaccination, see Section 10.5.6 for further details.

Note that for all summaries by SOC and PT, counting is by subject, not event and subjects are only counted once within each SOC and PT. However, if not stated otherwise, all summaries of unsolicited AEs include the number of AEs reported in each category and all events of a subject are then counted.

All AE summary tables are provided overall, by vaccine group (placebo, pooled CVnCoV lot, and split by lot), and are repeated separately in subjects seronegative at baseline and in subjects seropositive at baseline for SARS-CoV-2 N protein antibody levels (see Section 10.6.1).

In general, percentages are based on the number of subjects in the respective analysis set. In summary tables for AEs after the second vaccination, percentages are based on the number of subjects in the respective analysis set who have received the second vaccination.

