12.6.1.2 Analysis of Solicited AEs

The following summaries of solicited AEs within 7 days after each trial vaccination and within 7 days after any trial vaccination are planned:

- Summary of local and systemic AEs, overall and by maximum grade (mild / moderate / severe)
 - Are also provided by gender (female/male) for any vaccination, vaccination 1, and vaccination 2.

-
- Occurrence of local AEs, overall and by maximum grade (mild / moderate / severe)
 - Occurrence of systemic AEs, overall and by maximum grade (mild / moderate / severe)
 - Occurrence of related systemic AEs, overall and by maximum grade (mild / moderate / severe)
 - Duration (days) of local AEs, overall and for grade 3 events
 - Duration (days) of systemic AEs, overall and for grade 3 events
 - Duration (days) of related systemic AEs, overall and for grade 3 events
 - Daily summary of local AEs overall and by maximum grade (mild/moderate/severe) (only for each dose)
 - Daily summary of systemic AEs overall and by maximum grade (mild/moderate/severe) (only for each dose)
 - Daily summary of related systemic AEs overall and by maximum grade (mild/moderate/severe) (only for each dose)
 - Summary of time of onset (Day) overall and for grade 3 solicited AEs, any solicited AEs, local, systemic AEs, and related systemic AEs
 - Time of onset (Day) of local AEs, overall and for grade 3 events
 - Time of onset (Day) of systemic AEs, overall and for grade 3 events.
 - Time of onset (Day) of related systemic AEs, overall and for grade 3 events

All analyses of solicited AEs are provided based on the SASsol.

In agreement with the sponsor was decided to not provide any analyses on solicited AEs in the EOT analysis. Therefore some of the above analyses are never performed. For details, please refer to Appendix 4.

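### By-dose solicited AE percentages keep dosed subjects with no diary for that dose in the denominator, so those rates can only be biased down, by an amount the documents do not fix

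*SAP*

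**What the plan says.** Solicited local and systemic AEs within 7 days after each vaccination are primary safety endpoints (Protocol 4.2.1; SAP 9.1.1).

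- **Entry to the set.** SASsol takes Immunogenicity/Reactogenicity subjects "with at least 1 diary collection indicating the occurrence or lack of occurrence of solicited AEs" (SAP 9.5.3). SAP 10.5.2 makes this operational: "If at least one question on occurrence of a local or systemic AE is answered with either" yes or no, the subject is in. It adds that "the inclusion in the SASsol is defined overall, not by trial vaccine dosing". Its own example is a subject with information after dose 2 "but not for the time period after the first vaccination, the subject is still included in the SASsol".
- **Use of the set.** "All analyses of solicited AEs are provided based on the SASsol" (SAP 12.6.1.2).
- **Denominator.** Under SAP 12.6.1 the general base is the whole analysis set; after dose 2, "percentages are based on the number of subjects in the respective analysis set who have received the second vaccination".
- **Numerator.** SAP 10.5.2 takes solicited AEs from the CRF, with diary data used to decide SASsol eligibility. It also says: "Note that events with a severity Grade 0 are not recorded as AEs in the CRF".
- **Missing data.** Protocol 10.3.9 sets a valid-case principle and says "No imputation of missing values will be done for any analysis", apart from partial dates.
- **Scope.** SAP 12.6.1.2 drops all solicited AE analyses from the end-of-trial delivery and refers to Appendix 4, which is kept outside the SAP.

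**The concern.** SASsol exists because a subject who never answered a solicited question says nothing about solicited reactions. The plan applies that logic once per subject, although the endpoint is reported once per dose. The dose-2 rule removes subjects who were not dosed. It does not remove subjects who were dosed but not observed.

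Because Grade 0 is not entered on the CRF, a diary reporting no reaction and a missing diary look the same in the data that feed the tables. Both add one to the denominator and nothing to the numerator. The by-dose rates of a primary safety endpoint would then be understated, and the tables as described would give no sign of it, since no diary completion by dose is specified.

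**Working it through.** **The plan's own figure.** For the 840 CVnCoV subjects planned in the subset (SAP 8.5.1), the chance of seeing at least one AE at a true 5:1000 is 1 − 0.995^840 = 98.5%, as stated. With zero events, the one-sided 95% bound is 1 − 0.05^(1/840) = 3.56:1000, stated as 3.6. Both treat all 840 as informative after the dose.

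**Notation, for one dose.**
- p: true reaction rate among dosed SASsol subjects
- m: share of them with no diary for that dose
- q: true reaction rate in that no-diary share
- c: share of their reactions that still reach the CRF

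The documents give none of these, so every value below is an assumption.

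**Direction.** All dosed SASsol subjects stay in the denominator, so only the unrecovered reactions are lost:

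reported rate = p − m(1 − c)q

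The lost term is never negative. Against the true rate in dosed subjects, the reported rate is therefore too low or exact, whatever the reason for missingness.

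**Size when missingness is unrelated to reaction (q = p).**

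reported rate = p × [1 − m(1 − c)]

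| m (assumed) | true 50%, c = 0 | true 50%, c = 0.5 | true 80%, c = 0 | true 80%, c = 0.5 |
|---|---|---|---|---|
| 5% | 47.5% | 48.75% | 76% | 78% |
| 10% | 45% | 47.5% | 72% | 76% |
| 20% | 40% | 45% | 64% | 72% |

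Example: m = 10%, c = 0.5 gives 0.50 × (1 − 0.10 × 0.5) = 0.475. At c = 1 the factor is 1 and there is no bias.

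**Effect on detection.** Informative n falls from 840 to 798, 756 or 672 at m = 5, 10 or 20%. The 5:1000 detection probability becomes 98.2, 97.7 or 96.6%, and the zero-event bound 3.8, 4.0 or 4.5 per 1000. This is small; the issue is the reported percentages.

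**A denominator that would go wrong the other way.** Suppose no-diary subjects were admitted only if they had an investigator-recorded event. With p = 50% and full recovery, m = 10% gives 0.50 / (0.90 + 0.10 × 0.50) = 0.50/0.95 = 52.6%, and m = 20% gives 0.50/0.90 = 55.6%. Inclusion would depend on the outcome and push rates up.

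**The case against.** The strongest case for the plan has four parts.

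- **The set is the protocol's own.** Protocol 10.2.2 defines SASsol by one diary collection with no per-dose condition, and the SAP states the consequence openly with an example. The protocol estimand is the percentage of subjects reporting each AE among dosed subset subjects, which fits an all-dosed denominator. This stands as far as it goes: the SAP does not depart from the protocol's definition. It does not make an unobserved dose informative.
- **The diary is not the only route to the CRF.** Investigators may add solicited AEs when a diary is judged incomplete (SAP 10.5.2), and staff review solicited AEs on Days 2, 29, 30 and 43 (Protocol 9.1.1). This also stands, and it is why c appears in the formula. Addition is discretionary, so full recovery cannot be assumed. A reader might infer that no diary means no CRF entry; the documents do not support that.
- **No explicit prohibition.** A reader might infer a silent imputation that the protocol forbids. Protocol 10.3.9 states its valid-case principle for vaccination variables, and the SAP imputes no value. The denominator sits badly with the principle but breaks no express rule.
- **Scope and timing.** The end-of-trial delivery contains no solicited analyses, so correction means rerunning earlier outputs under a SAP whose authors were unblinded (SAP 6.0). This limits where the point applies. The end-point definitions are unchanged, and SAP 6.0 and 12.6.6 refer to earlier safety deliveries.

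A reader might also infer that strong reactors after dose 1 stop completing the diary. The documents give no data on this, and the downward direction does not need it.

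**Conclusion.** The point holds in a limited form. As written, the rules leave dosed subjects with no diary for a dose in that dose's denominator as apparent non-reactors unless a reaction reached the CRF another way. The bias in the by-dose rate has one direction, down. Its size is unknown because no completion or recovery rate is given. At an assumed m of 10%, a true 50% loses 5 points with no recovery, 2.5 with half and none with full recovery, provided missingness is unrelated to reaction.

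If m and c are similar across arms, the difference from placebo shrinks by about the same factor; if they differ, it can be distorted either way. The end-of-trial tables are not affected. The point matters for earlier safety deliveries and for any solicited table carried into the clinical trial report.

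**What to change.** - **By-dose tables.** Use as denominator the SASsol subjects who received that dose and gave at least one yes/no solicited diary answer in the 8-day window after it (vaccination day plus 7 days). Restrict the numerator to the same subjects.
- **Daily tables.** Require an answer for that day; one answer elsewhere in the window is not enough.
- **No entry through an event.** Do not admit a subject because a reaction was recorded.
- **Display.** Print the evaluable n and diary completion by dose and arm.
- **Sensitivity.** Keep the current all-dosed SASsol version, which includes investigator-recorded events in no-diary subjects. It is a floor for the true rate. The evaluable version can itself be off if missingness relates to reaction, so the two should be shown together; that also removes any choice made after unblinding.

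The diary answers already decide SASsol membership, so no new data are needed. The cost is dose-level and day-level flags, slightly smaller denominators, and a rerun of the affected tables from earlier deliveries.

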10.5.3 Duration and Time of Onset for Solicited AEs

Duration of solicited local and systemic AEs is defined as the number of **consecutive** days with a recorded local/systemic AE regardless of grade. For example, Fatigue with Grade 1 occurring on day 2 and 3 and day 7 is counted as two separate events with the duration 2 days and 1 day.

The duration of solicited local and systemic AEs ongoing beyond Day 8 after vaccination is defined as

$$\text{Duration} = \text{AE end date} - \text{AE start date} + 1.$$

The AE end date as recorded on the CRF is used in the above formula except for instances where the recorded date is incomplete in which case the imputed date is used.

The time of onset (Day) of a solicited AE is defined as the day of first occurrence of the AE after the trial vaccination it was assigned to (dose 1 or dose 2, see also Section 10.5.2), regardless of the severity (Grade 1 – Grade 3). The time of onset (Day) of a Grade 3 solicited AE is defined as the first day after the trial vaccination it was assigned to (dose 1 or dose 2, see also Section 10.5.2), on which the AE was first graded as severe (Grade 3), regardless of an earlier occurrence with a lower severity.

Durations are not calculated separately for each grade but rather only for any grade >0 (no matter how often it might transition up and down between grades 1 through 3) or grade=3. Only the longest consecutive duration determined this way is displayed.

Duration and time of onset are calculated separately for events recorded after each trial vaccination.

10.5.4 Unsolicited AEs

Information on unsolicited AEs occurring on each vaccination day (i.e. dose 1 and 2) and the following 28 days after each dose is collected for subjects in the Immunogenicity/Reactogenicity subset. Data is recorded in the eDiary by the subject to aid AE reporting. The investigator reviews the eDiary and records information on any AEs on the CRF.

Unsolicited AEs are assigned to first or second dose based on the (reported or imputed) AE date. Unsolicited AEs occurring before dose 2 are assigned to dose 1. Unsolicited AEs occurring after dose 2, are assigned to dose 2. Unsolicited AEs occurring on the day of dose 2 are assigned to either dose 1 or dose 2 as per the following rules:

- If the AE occurred on the day of dose 2 but before vaccination with dose 2, the AE is assigned to dose 1
- If the AE occurred on the day of dose 2 but on or after vaccination with dose 2, it is assigned to dose 2.
- If the AE occurred on the day of dose 2 and it cannot be determined whether it occurred before, on or after vaccination with dose 2, it is assigned to dose 2.

10.5.5 Adverse Events of Special Interest

The following events are considered and collected as AESI throughout the trial:

- AEs with a suspected immune-mediated etiology (pIMDs, see Appendix 1)
- Other AEs relevant to SARS-CoV-2 vaccine development or the target disease (see Appendix 2)

AESI are identified as recorded by the investigator in the eCRF (electronic CRF). No additional programming is performed to identify (potential) AESIs.

10.5.6 Medically Attended AEs

Up to 6 months after second vaccination (or up to EOT, whatever is earlier), subjects are asked to confirm if they sought medical attention for an AE. Medically attended AEs are defined as AEs with medically-attended visits that are not routine visits for physical examination or vaccination, such as visits for hospitalization, an emergency room visit, or an otherwise unscheduled visit to or from medical personnel (medical doctor) for any reason. The start of a medically attended AE is defined by its start date, irrespective of the date medical attention was sought. A medically attended AE is considered as occurring up to 6 months after second trial vaccination if

$$\text{Start Date of AE} - (\text{Scheduled}) \text{ date of second vaccination} + 1 \leq 180 \text{ days.}$$

I.e. one month is defined as 30 days and the date of the scheduled second vaccination (Day 29) is used in case a subject only received the first vaccination.

10.5.7 Adverse Events Related to Standardized and Customized MedDRA Queries

Subjects' AEs are filtered with Standardized MedDRA Queries (SMQs) and Customized MedDRA Queries (CMQs) for the following SMQs/CMQs:

- Anaphylactic reaction (SMQ)
- Convulsions (SMQ)
- Embolic and thrombotic events
- Hypersensitivity (SMQ)
- Immune-mediated/autoimmune disorders (SMQ)
- Liver related investigations, signs and symptoms (Sub-SMQ)
- Paraesthesia, Hypoaesthesia, Hyperaesthesia (CMQ)
- Taste and smell disorders (CMQ)

The related terms for MedDRA Version 23.1 are listed in Appendix 3.

10.5.8 Overreported AEs

The definition of overreported AEs consists of the following 6 items:

No overreporting restrictions exist for:

1. (Treatment emergent) AESIs
2. (Treatment emergent) SAEs
3. (Treatment emergent) non-serious intercurrent medical condition that may affect the immune response to vaccination
4. (Treatment emergent) AEs leading to vaccine withdrawal or trial discontinuation

Overreporting restrictions:

5. Medically attended TEAEs not matching any of the above 4 categories that have started later than 6 months after 2nd dose
6. TEAEs not matching any of the above 5 categories that have started later than 28 days after any dose. (I.e. An AE starting between Day 29 and 49 when dose 2 was given on Day 50 is also an overreported AE.)

In the output, overreported AEs are displayed in listings but are not included in tables.

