### 9.3.3.2 Unsolicited Adverse Events and Serious Adverse Events

Unsolicited AEs occurring on the day of vaccination and the following 28 days will be recorded by subjects included in the Immunogenicity/Reactogenicity Subset for each of the 2 trial vaccinations.

For all subjects, medically-attended AEs will be collected through 6 months after the second trial vaccination. AESIs will be collected through 1 year after the second trial vaccination (see Section 9.3.3.3). SAEs will be collected through 1 year after the second trial vaccination.

Medically-attended AEs are defined as AEs with medically-attended visits that are not routine visits for physical examination or vaccination, such as visits for hospitalization, an emergency room visit, or an otherwise unscheduled visit to or from medical personnel (medical doctor) for any reason.

The occurrence of AEs (serious and non-serious) will be assessed by non-directive questioning of the subject at each visit. AEs volunteered by the subject during or between visits as eDiary entries or detected through observation, physical examination, laboratory test, or other assessments during the entire trial, will be recorded in the eCRF if they fulfil the definitions as specified in section 9.3.2. Subjects should be instructed to report immediately any AEs with serious symptoms, subjective complaints or objective changes in their well-being to the Investigator or the site personnel, regardless of the perceived relationship between the event and the trial vaccine.

The Investigator will assess the relationship between trial vaccine and occurrence of each AE/SAE.

Non-serious intercurrent medical conditions that may affect the immune response to vaccination will also be collected throughout the trial.

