### 10.3.5 Safety Analysis

No formal statistical testing of safety data is planned.

Safety endpoints will be described for each CVnCoV lot separately, for pooled lots, for placebo and overall.

**Solicited AEs:** The frequencies and percentages of subjects experiencing each solicited local and systemic AE within 7 days after each vaccination will be presented by intensity and overall. For subjects with more than 1 episode of the same AE within 7 days after a vaccination, the maximum intensity will be used for tabulations. Similar tabulations will be performed for solicited systemic AEs by relationship to trial vaccination. Solicited local AEs will be by definition considered as related to the trial vaccine. Time to onset (in days) and duration (in days) will also be summarized for each solicited local and systemic AEs. Summary tables showing the occurrence of at least 1 local or systemic solicited AE within 7 days after each vaccination will also be presented.

**Unsolicited AEs:** Unsolicited AEs including SAEs and AESIs will be coded using the Medical Dictionary for Regulatory Activities (MedDRA) by SOC and PT.

The frequency and percentage of subjects reporting at least 1 unsolicited AE within the 28 days after each vaccination and overall will be tabulated globally and for each SOC and PT levels.

Similar tables will be provided for: related unsolicited AE, Grade 3 or higher unsolicited AE, medically-attended AEs that occur within 6 months after the second trial vaccination, SAE, related SAE, AESI, related AESI, AEs leading to withdrawal or trial discontinuation and SAE resulting in death through 1 year after the second trial vaccination.

When an AE occurs more than once for a subject within the 29 days post 1 vaccination, the maximal severity and strongest relationship to the vaccine group will be counted.

Only AE post first vaccination will be considered in the summary tables. AE starting prior to the first vaccination will only be listed.

Data listings of fatal and SAEs will be provided by subject.

Vital signs will be summarized by descriptive statistics at each visit including change from baseline and a listing will be provided.

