9.0 Trial Endpoints

9.1 Primary Endpoints

9.1.1 Primary Safety Endpoints

- Occurrence, intensity and relationship of medically-attended AEs collected through 6 months after the second trial vaccination in all subjects.

-
- Occurrence, intensity and relationship of SAEs and AESIs collected through EOT Visit in all subjects.
 - Occurrence of fatal SAEs through EOT Visit in all subjects.
 - Occurrence of AEs leading to vaccine withdrawal or trial discontinuation through EOT Visit in all subjects.
 - Occurrence, intensity and duration of each solicited local AE within 7 days after each trial vaccination in a subset of subjects.
 - Occurrence, intensity, duration of each solicited systemic AE within 7 days after each trial vaccination in a subset of subjects.
 - Occurrence, intensity and relationship of unsolicited AEs occurring within 28 days after each trial vaccination in a subset of subjects.

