10.2 Trial Day

Throughout this trial, trial days are defined as follows:

- Day 1 is the day of first trial vaccination.
- For days after first trial vaccination, trial day is calculated as

$$\text{Trial Day} = \text{Date of day} - \text{Date of first vaccination} + 1.$$

- For days before first trial vaccination, trial day is calculated as

$$\text{Trial Day} = \text{Date of day} - \text{Date of first vaccination.}$$

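### The worked example in SAP 10.5.8 item 6 classes Day 29 as overreported, although the rule it illustrates and the collection window both keep Day 29 in

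*SAP*

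**What the plan says.** **Day count.** SAP 10.2 states that "Day 1 is the day of first trial vaccination" and numbers later days as date minus first vaccination date plus 1.

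**Collection window.** Protocol 9.3.3.2: "Unsolicited AEs occurring on the day of vaccination and the following 28 days will be recorded by subjects included in the Immunogenicity/Reactogenicity Subset". SAP 10.5.4 repeats this: "Information on unsolicited AEs occurring on each vaccination day (i.e. dose 1 and 2) and the following 28 days after each dose is collected". Protocol 10.3.5 gives the window its full length when it deals with repeated events: "When an AE occurs more than once for a subject within the 29 days post 1 vaccination".

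**Endpoint.** SAP 9.1.1 lists as a primary safety endpoint: "Occurrence, intensity and relationship of unsolicited AEs occurring within 28 days after each trial vaccination in a subset of subjects".

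**Overreporting rule.** Item 6 of SAP 10.5.8 covers "TEAEs not matching any of the above 5 categories that have started later than 28 days after any dose". A bracketed illustration follows: "An AE starting between Day 29 and 49 when dose 2 was given on Day 50 is also an overreported AE". The section closes by sending overreported AEs to listings only, not to tables. Items 1 to 4 exempt AESIs, SAEs, non-serious intercurrent conditions that may affect the immune response, and AEs leading to vaccine withdrawal or trial discontinuation.

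**The concern.** The rule and its illustration give different first days. The rule starts the exclusion after the 28th day following the dose; the illustration starts it on that 28th day. A programmer who codes the sentence and one who codes the example would produce different tables for a primary safety endpoint, and the second would leave out events that the protocol collects inside the window. Because the illustration is the only place in the section where the rule is turned into trial days, it is a natural thing to program from.

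**Working it through.** **Inputs**
- Dose 1 = Day 1; trial day = date − date of dose 1 + 1 (SAP 10.2).
- Window: dose day plus the following 28 days (Protocol 9.3.3.2, SAP 10.5.4).
- Rule: overreported if start is more than 28 days after the dose (SAP 10.5.8 item 6).
- Example: dose 2 on Day 50, overreported interval Day 29 to Day 49 (same item).
- Dose 2 visit: Day 29, −3/+7 days, so Days 26 to 36 (Protocol 9.1.1.3).

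**Step 1: the plan's own example.** Taken inclusively, Day 29 to Day 49 is 49 − 29 + 1 = 21 days.

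**Step 2: the rule.** Overreported if start day − 1 > 28, so start day ≥ 30. Before a dose 2 on Day 50 that gives Days 30 to 49, or 49 − 30 + 1 = 20 days. The example is one day too long, at its start.

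**Step 3: can the example be read to fit?**
- Exclusive endpoints give Days 30 to 48, or 19 days. That rescues Day 29 but drops Day 49, which is 48 days after dose 1 and before dose 2, and so is overreported under the rule. Neither reading reproduces 30 to 49.
- Counting the dose day as day 1 of 28 (start − dose + 1 > 28) does give Day 29. But that is a 28-day window, whereas the window is the dose day and 28 more: 1 + 28 = 29 days, the figure in Protocol 10.3.5.

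**Step 4: consistency elsewhere.** The solicited-AE window is the dose day plus 7 days, and SAP 10.5.3 speaks of events that continue past Day 8 (1 + 7 = 8). The same pattern for unsolicited AEs gives 1 + 28 = 29 as the last day in.

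**Step 5: who is affected.**

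| Dose 2 | Status of Day 29 under the example |
|---|---|
| Days 26 to 28 | inside the dose 2 window; not affected |
| Day 29 | dose 2 day itself; not affected |
| Days 30 to 36 (in window) or later | classed as overreported |
| never given | classed as overreported, if the example's count is carried over |

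**Step 6: size.** One day of 29: 1/29 = 3.4% of the dose-1 window, for affected subjects only. These windows apply to the Immunogenicity/Reactogenicity Subset (the first 1,260 enrolled).

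**The case against.** The strongest reply is that the operative sentence of item 6 is right and only a bracketed illustration, for a hypothetical dose 2 on Day 50, is wrong. The 28-day window is stated correctly elsewhere, and correct code would follow the sentence. That stands: this is an internal contradiction whose effect depends on which text is programmed, and the documents do not show which was.

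The consequence is also limited. The most important event classes are exempt, and dropped events still appear in listings. In addition, SAP 12.6.1.1 plans tables of all reported unsolicited AEs, including those starting after 28 days. That sits awkwardly with the listings-only rule, but it means a Day 29 event might still be tabulated there. None of this makes the example correct.

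A reader might go further and infer a second counting slip in SAP 10.5.6. That section counts a medically-attended AE only if start − dose 2 + 1 ≤ 180, so the last counted day is dose 2 + 179. With dose 2 on Day 29 this is Day 208, three days before the Day 211 visit (29 + 182) at which these events are still collected. The documents do not support calling this an error:
- The protocol never converts 6 months into days. SAP 10.5.6 does so openly: "I.e. one month is defined as 30 days and the date of the scheduled second vaccination (Day 29) is used".
- Day 211 is a visit date with a −7/+7 window, not a stated end of the endpoint.
- The gap is not the same for everyone. The cut-off follows the dose 2 date: Day 205 for dose 2 on Day 26, and Day 215, after the nominal visit, for dose 2 on Day 36.
- In the main safety tables, subjects censored at unblinding or authorized-vaccine receipt (SAP 10.10, 12.6.7) before dose 2 + 179 lose nothing to the rule.

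**Conclusion.** The example in SAP 10.5.8 item 6 is wrong as written. It contradicts the rule it explains and the window both documents use for a primary safety endpoint. If coded from the example, the tables lose Day 29, 1 of the 29 dose-1 window days, for subset subjects whose dose 2 came after Day 29 or was never given.

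The effect is small. It touches one day, in some subjects of the subset, for events outside the four exempt classes, and those events remain in the listings. The documents give no event counts and no distribution of dose 2 dates, so the number of events cannot be calculated; few are likely to be affected. The size given assumes that the example's count is applied to dose 1 for every subject without dose 2 by Day 29. The example says nothing about the end of the dose 2 window, so no loss is counted there.

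The 180-day rule for medically-attended AEs is a declared convention and no part of this error.

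**What to change.** In SAP 10.5.8 item 6, start the example's interval at Day 30, so that it runs from Day 30 to Day 49 for a dose 2 on Day 50. If any code was written from the example, check that the flag uses start date minus dose date greater than 28. The cost is one number in the SAP and one line of program review; no data, endpoint or analysis set changes.

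Optionally, list the 180-day definition of 6 months in SAP 6.1, since it closes three days before the nominal Day 211 visit when dose 2 is on Day 29. The formula itself need not change.
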